8. SAFETY ANALYSES

8.1 Exposure to study treatments

Exposure to study treatments will be calculated as date of last treatment minus date of start of treatment + 1. If unknown, date of last treatment will be estimated and imputed. Exposure will be summarised using descriptive statistics and tabulated by treatment group. For this and the other safety analyses described in this section, the populations displayed will be the Safety population and ET sub-group.

8.2 Adverse events

Adverse events will be coded by MedDRA SOC and Preferred Term, and summarised and tabulated for the safety population. For each Preferred Term the number and percent of subjects reporting each adverse event will be tabulated by treatment group. These tables include:

- Adverse event summary table
- Adverse events occurring prior to study treatment, if any
- All treatment-emergent adverse events
- Most common (>5%) treatment-emergent adverse events in any group
- Treatment emergent adverse events that were possibly, probably or definitely related to the study medication (if large study then only the most common of these may be presented in Section 12 tables)
- Severe adverse events
- Adverse events causing withdrawal
- All adverse events by maximum severity and relationship to study treatment, with subject identification. (ICH format)

Odds ratios will be calculated for the 15 most commonly reported Preferred Terms.

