#### **7.3.2 Physical Examination and Targeted Examination**

A complete physical examination will include head, ears, eyes, nose, throat, heart, lungs, abdomen, lymph nodes, musculoskeletal and neurological assessment and skin. Genitourinary system will be examined only when clinically indicated.

A targeted physical examination will be performed throughout the study to determine physical findings of systems appropriate to assessing the clinical status of the subject relative to study treatment and their disease. In particular, subjects will be monitored throughout the study for gastrointestinal events. Other body systems should be examined as clinically indicated.

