### **10.7 Warnings and Precautions**

The adverse event profile in humans is IMM-124E has not been fully characterized. In clinical trials and commercial use at doses equal or lower than those used in this study, IMM-124E was well tolerated with a safety profile expected of bovine colostrum. The most common adverse reactions expected include modified bowel movements and nausea.

For further information regarding warnings and precautions with the study drug, please refer to the Investigator's Brochure for Imm-124E.

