## 12.6 Analysis of Safety

### 12.6.1 Incidence of Adverse events

All AEs will be coded using the Medical Dictionary for Regulatory Activities (MedDRA). AEs will be summarized according to the number of subjects experiencing specific events, reported by system organ class, high level group term, high level term and preferred term. AEs will also be presented by severity and relationship to treatment. All data will be listed.

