3.3 General statistical methodology

Treatment groups will be described as '600 mg IMM-124E', '1200 mg IMM-124E' and 'Placebo'. All tables, figures and listings will be produced for these three treatment groups. In addition, where specified, tables will be produced where subjects are grouped by baseline hepatic fat fraction, baseline HbA1c, and with a binary classification (not treated vs. treated).

General descriptive statistics for continuous measures will include number of observations (n), mean, standard deviation (SD), median, quartiles, minimum and maximum. For categorical variables, descriptive statistics will include n and percentage occurrence within the treatment group. The denominator for calculating percentage will be the number of valid observations within the treatment group.

For the basic and interim analysis, missing data will remain missing and not be imputed. However, for sensitivity measures in the final study analysis, missing values will also be imputed using a multiple imputation technique (Berglund, 2010 and Yuan, 2011).

This is a multicentre study, but no analysis using centre as a stratification factor will be performed, except for the primary endpoint, in which case the analysis will be performed on the imputed data both with and without centre as a stratification factor as a sensitivity analysis on the primary endpoint. Analysis of centre as a stratification factor will also be performed on ALT, AST, Glucose, A_{1c}, lipid profile parameters and CK-18.

Concomitant medications will be coded using the most recently available version of the World Health Organisation Drug Dictionary (WHO DD) at the time of data lock. Medications will be summarised and tabulated using the first and second levels of the dictionary. Medical history and adverse events will be coded using the most recently available version of the Medical Dictionary for Regulatory Affairs (MedDRA) at the time of data lock. Both medical history and adverse events will be summarised and tabulated using System Organ Class and Preferred Terms.

Patients given the wrong treatment will be analysed as randomised for efficacy measures (for the ITT, PP and FAS populations) and as treated for safety measures (Safety population and ET subgroup).

For safety data, if there are unscheduled visits where data values exist and those data are missing for the prior, scheduled, visit, then the values from the unscheduled visit will be imputed.

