MELD score with change by visit with Fibrosis sub-groups as stratification factor (FAS population)

MELD score with change by visit with Fibrosis sub-groups as stratification factor (ITT population)

MELD score with change by visit with Fibrosis sub-groups as stratification factor (PP population)

MELD score with change by visit with Ballooning sub-groups as stratification factor (FAS population)

MELD score with change by visit with Ballooning sub-groups as stratification factor (ITT population)

MELD score with change by visit with Ballooning sub-groups as stratification factor (PP population)

MELD score with change by visit with Inflammation sub-groups as stratification factor (FAS population)

MELD score with change by visit with Inflammation sub-groups as stratification factor (ITT population)

	MELD score with change by visit with Inflammation sub-groups as stratification factor (PP population)
	MELD score with change by visit with ALT sub-groups as stratification factor (FAS population)
	MELD score with change by visit with ALT sub-groups as stratification factor (ITT population)
	MELD score with change by visit with ALT sub-groups as stratification factor (PP population)
Section 12.1	Exposure
Section 12.2	Adverse events summary
	Adverse events occurring prior to study treatment (if any) (Safety and ET populations)
	Most common ($\geq 10\%$) treatment emergent adverse events by Preferred Term (Safety population)
	Treatment emergent adverse events leading to withdrawal (Safety and ET populations)
	Exploratory table including baseline and final values (ET population)
Section 14.1	Medical history (Safety and ET populations)
	Physical Examination (Safety population)
	12-lead ECG (Safety population)
	Prior medications (Safety and ET populations)
	Concomitant medications (Safety and ET populations)
	New medications (Safety and ET populations)
	Urinalysis at Screening (Safety population)
Section 14.3	Treatment emergent adverse events (Safety and ET populations)
	Treatment emergent adverse events that were possibly, probably or definitely related to the study medication (Safety and ET populations)
	Serious adverse events (Safety and ET populations)
	Severe adverse events (Safety and ET populations)
	Treatment emergent adverse events by maximum severity and relationship to study treatment, with subject identification (Safety population)
Section 14.4	Serum Biochemistry by visit (Safety population)

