	Shift table of serum biochemistry by visit (Safety population)
	Haematology by visit (Safety population)
	Shift table of haematology by visit (Safety population)
	Vital signs by visit (Safety population)
	Physical examination results by visit

Figure Section	Figure Title (Population)
Section 11.4	
Difference in hepatic fat between Placebo and each dose level of IMM-124E (ITT, PP, FAS populations)
 
Difference in hepatic fat between Placebo and each dose level of IMM-124E by hepatic fat category and HbA1c (ITT, PP, FAS populations) (lattice graph)
 
Difference in hepatic fat between Placebo and each dose level of IMM-124E (ITT, PP, FAS populations with MI imputation where appropriate)
 
Difference in hepatic fat between Placebo and each dose level of IMM-124E by hepatic fat category and HbA1c (ITT, PP, FAS populations with MI imputation where appropriate) (lattice graph)
 
Proportion of subjects with normal ALT by visit (ITT, PP, FAS populations)
 
MELD score by visit (ITT, PP, FAS populations)
 
Proportion of subjects with 5% reduction of hepatic fat from baseline (ITT, PP, FAS populations)
 
Proportion of subjects with 10% reduction of hepatic fat from baseline (ITT, PP, FAS populations)
 
Body mass index, waist circumference and waist:hip ratio by visit (ITT, PP, FAS populations)
 
HbA1c by visit (ITT, PP, FAS populations)
 
HOMA-IR by visit (ITT, PP, FAS populations)
 
AUDIT results by visit (ITT, PP, FAS populations)

Section 12.2	Odds ratios of most common Preferred Terms (Safety population)

Sample Tables

Primary analysis

										Group comparisons					
Treatment	Visit / Value	n	Mean	SD	Median	Quartiles 1 & 3	Min	Max	Prob = 0	Normality Prob	Change	Ranks Prob	Ranks	Permut ations	Disp- arity
Treatment 1	Screening														
	Baseline														
	Timepoint 1														
	Change to Timepoint 1														
	Adj change to Timepoint 1 Difference from Treatment 2														
	Difference from Treatment 3														
	Change to Timepoint 2...														

Primary analysis with Subgrouping

Subgroup (e.g. HFF, A1c, ALT, Fibrosis, Inflammation, ballooning)	Treatment	Visit / Value	n	Mean	SD	Median	Quartiles 1 & 3	Min	Max	Prob = 0	Group comparisons					Disparity	
											Normality Prob	Change	Ranks Prob	Ranks	Permutations		
Group 1	Treatment 1	Screening															
		Baseline															
		Timepoint 1															
		Change to Timepoint 1															

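### The only effect measure planned for adverse events is an odds ratio per Preferred Term, with no interval or zero-cell rule and no estimate for the expected bowel reactions as a group

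*SAP*

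**What the plan says.** Safety is a primary endpoint (protocol 4.2), assessed by the incidence and severity of adverse events together with vital signs and laboratory changes. The protocol names the harm in advance: "The most common adverse reactions expected include modified bowel movements and nausea" (10.7). It also directs the targeted examinations to it: "In particular, subjects will be monitored throughout the study for gastrointestinal events" (7.3.2).

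Protocol 12.6.1 promises subject counts at four MedDRA levels, "reported by system organ class, high level group term, high level term and preferred term". The SAP keeps two of them: "Both medical history and adverse events will be summarised and tabulated using System Organ Class and Preferred Terms" (3.3). SAP 8.2 adds "For each Preferred Term the number and percent of subjects reporting each adverse event will be tabulated by treatment group", and lists tables for all treatment-emergent, common, related and severe events and for events leading to withdrawal.

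The one effect measure is in the last line of SAP 8.2: "Odds ratios will be calculated for the 15 most commonly reported Preferred Terms". It appears in the only safety figure listed in SAP 12, "Odds ratios of most common Preferred Terms (Safety population". Neither place gives the contrast, an interval or a rule for an empty cell. SAP 3.3 also allows a treated versus not-treated grouping where specified, so the odds ratios could be per dose or pooled.

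The cut-off for common events differs within the SAP. Section 8.2 uses more than 5% in any group. The table list uses at least 10% for the common "treatment emergent adverse events by Preferred Term (Safety population" table.

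**The concern.** A harm is named in advance and safety is primary, yet the plan contains no effect estimate for that harm. Modified bowel movements is a description and may be coded to several Preferred Terms. If so, its cases are divided among them before any odds ratio is calculated. The high level group term and high level term rows, which could bring related bowel terms together, are in the protocol but not in the SAP. SAP 10 only says that changes will be documented in the final study report.

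An odds ratio on small counts is also fragile. When placebo has no case the sample value is infinite, and when neither arm has one it is undefined. The SAP has no rule for either situation and plans no interval to show how imprecise the rest are. At stake is a primary safety question for which a useful summary, how many more subjects per hundred have a gastrointestinal reaction on each dose, would have to be chosen after unblinding.

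**Working it through.** **The plan's own figures.** The documents give no power or precision figure for adverse events. Their one power statement (about 85%, protocol 12.1) concerns liver fat. It reproduces: SD of change = √(2 × 6² × (1 − 0.25)) = 7.35, and a two-sided t-test with 40 per arm and a difference of 5 has 85.2% power (85.7% with SD 7.3). It does not bear on this point.

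**Inputs.** At least 40 subjects per arm (protocol 5.2). Expected rates in this trial: not given. Protocol 3.5.1.2 cites 1/8 (12.5%) for mild diarrhea and 1/24 (4.2%) for nausea and vomiting from earlier colostrum studies. All rates below are assumptions.

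**Empty placebo cell.** P(no case in 40) = (1 − p)^40:
- p = 1%: 67%
- p = 2%: 45%
- p = 2.5%: 36%
- p = 5%: 13%
- p = 10%: 1.5%

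If a 10% placebo rate is split into four exclusive terms of 2.5%, at least one has no placebo case in about 84% of trials.

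**What an empty cell does.** Take 6/40 v 0/40. The odds ratio is infinite, with an exact 95% interval from 1.27 to infinity. The risk difference is 15 points, with a Newcombe score 95% interval of 3 to 29, finite at both ends.

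**Splitting the grouped event.** The table gives power of a two-sided Fisher test at 0.05, 40 v 40. The first power column is exact. The others are simulated, with the event divided equally over terms and each subject having at most one; they show the chance that at least one term reaches 0.05.

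| Assumed rates, active v placebo | Grouped event | Any of two terms | Any of four terms |
|---|---|---|---|
| 30% v 10% | 53% | 34% | 12% |
| 35% v 10% | 72% | 52% | 22% |
| 40% v 10% | 85% | 68% | 34% |

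The one-term-per-subject assumption matters. If a subject may have several terms, independently and with the same any-event rate, each of k terms has rate 1 − (1 − p)^(1/k), and the chance that any reaches 0.05 is 1 − (1 − power per term)^k. At 35% v 10% this gives about 61% for two terms and 34% for four.

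**One concrete trial.** 14/40 v 4/40 has p = 0.014, an odds ratio of (14 × 36)/(4 × 26) = 4.8, and a risk difference of 25 points (95% interval 7 to 42). Divided over four terms it becomes 4/40 v 1/40 twice (odds ratio 4.3, p = 0.36) and 3/40 v 1/40 twice (odds ratio 3.2, p = 0.62). The point estimates remain fairly close. Splitting costs precision, and without intervals the figure would not show that.

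**Cut-off for common events.** With 40 per arm, at least 10% means 4 or more subjects and more than 5% means 3 or more (2/40 is exactly 5%). In the 35% v 10%, four-term example, 52% of terms fall below the first cut-off in both arms and 28% below the second.

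**The case against.** The strongest reply is that the safety analysis is descriptive. Protocol 12 says the trial is meant to describe safety, and neither document plans a significance test on adverse events. Power at 0.05 is therefore a yardstick that the plan never adopted. This stands. The power figures show only how much information splitting loses.

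A reader might infer that the odds ratio is the only comparison between arms, or that the expected harm is likely to be missed. The documents do not support either reading. Numbers and percentages are tabulated by treatment group per Preferred Term, and SAP 3.3 adds System Organ Class. The gastrointestinal row should therefore show placebo and both doses side by side. The table of all treatment-emergent events has no frequency cut-off. An infinite odds ratio does not hide the counts either: it arises when every case is on active drug, its lower limit can still be given, and a one-sided limit can be plotted.

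The size of the loss also rests on assumptions. The rates of 35% and 10% appear nowhere in the documents. How bowel events will be coded cannot be told from them, and protocol Appendix A grades diarrhea in one row and nausea with vomiting in another. Nor does grouping cure a small sample. At 25% v 10% the grouped power is only 33%, and 80% power would need 100 per arm by the pooled-variance formula (62 at 30% v 10%).

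The reply leaves three gaps open: the odds ratio is unspecified, the expected harm has no effect estimate, and the SAP and protocol disagree on MedDRA levels.

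**Conclusion.** The point holds as a gap in specification. The sole effect measure for adverse events is a Preferred Term odds ratio with no stated contrast, interval or zero-cell rule. The harm expected in protocol 10.7 has no pre-specified effect estimate. Two summary levels required by protocol 12.6.1 are absent from the SAP, and the cut-off for common events is inconsistent.

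The firmest number is the empty-cell probability, 36% at a true placebo rate of 2.5%, which needs only the arm size and an assumed rate. The comparison of 72% with 22% to 52% is illustrative. It assumes full arms of 40, rates of 35% v 10%, and an equal split into four or two exclusive terms.

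The stronger conclusion, that harm would be concealed, does not follow, because the grouped counts remain visible by arm. This is a minor-to-moderate improvement to make while the data are still blinded.

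**What to change.** Amend SAP 8.2 and the table list before any unblinding, including the interim analysis in SAP 9, which has a safety purpose. A grouping chosen afterwards would be data-driven.

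- (a) Restore the high level group term and high level term rows of protocol 12.6.1.
- (b) For each dose versus placebo, pre-specify two proportions of subjects: those with any treatment-emergent event in the gastrointestinal System Organ Class, and those with any event in a grouping of the expected reactions whose terms are listed in advance. Report each descriptively as a risk difference with an exact or score 95% confidence interval.
- (c) Give risk differences with intervals beside the Preferred Term odds ratios, or in their place. If the odds ratios stay, state the contrast, the interval method and the handling of empty cells.
- (d) Use one cut-off for common events in SAP 8.2 and the table list.

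The events are already to be coded in MedDRA, so the cost is some SAP wording and slightly longer tables. No dose, schedule, visit or clinical rule changes.

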8.3 Serious adverse events

Serious adverse events will be tabulated in the same way as all adverse events. In addition, anecdotal descriptions of each serious adverse event will be provided.

8.4 Vital signs

Vital signs, including resting pulse, systolic and diastolic blood pressures, respiratory rate, and body temperature will be summarised with change from Baseline and tabulated by visit and treatment group.

8.5 Laboratory safety measurements

Serum biochemistry parameters will be summarised with change from Baseline and the count of clinically significant values and tabulated by visit. If multiple units are reported in the eCRF, values will be transformed to SI units prior to summary. Additionally, a serum biochemistry shift table, showing the number of normal values, abnormal (both above and below normal range) but not clinically significant, clinically significant (both above and below normal range) at Baseline and each visit during the treatment and follow-up periods will also be produced. Parameters summarised and tabulated in lipid panel, biomarkers and regulatory T cell tables will be excluded.

Haematology parameters will be summarised with change from Baseline and the count of clinically significant values and tabulated by visit. Additionally, a haematology shift table, showing the number of normal values, abnormal (both above and below normal range) but not clinically significant clinically significant (both above and below normal range) at Baseline and each visit during the treatment and follow-up periods will also be produced.

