#### 3.5.1.2 Safety Dose Modeling

IMM-124E is well tolerated in clinical studies and in the market place. While the typical dose for traveler's diarrhea is 600mg/day, doses as high as 10g four times daily have been studied. Adverse reactions have been few in number and mild in severity. In most clinical studies of bovine colostrum, there have been no treatment related adverse events reported and no clear pattern in events [Tacket *et al.*, 1992; Shield *et al.*, 1993; Mitra *et al.*, 1995; Sarker *et al.*, 1998; Huppertz *et al.*, 1999; Opekun *et al.*, 1999].

Adverse events observed include:

- nausea, flatulence [Rump *et al.*, 1992; Plettenberg *et al.*, 1993]
- nausea and vomiting in 1/24 patients [Greenberg and Cello 1996]
- mild diarrhea in 1/8 adult volunteers [Lissner *et al.*, 1998]

Tacket *et al.* (1988) reported no adverse clinical signs, but transient moderate elevations in serum levels of hepatic transaminases in volunteers who received bovine immunoglobulin concentrates prepared against *E. coli* (5/10) and rotavirus (2/10). This effect was attributed to diets high in protein provided at the hospital. Colostrum administration should be avoided in person allergic to cow's milk or with lactose intolerance.

The known safety profile of bovine colostrum gives a substantial therapeutic index. Therefore, the highest dose to be evaluated will be 3600mg/day.

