**Table 3: Safety Laboratory Parameters**

Test	Parameters
Hematology (Screening, Baseline, D7, D14, W4 and 4 weekly thereafter)	Hemoglobin, hematocrit, red blood cell (RBC) and RBC morphology, white blood cell (WBC) and differential WBC count, platelet count, mean corpuscular volume (MCV), mean corpuscular hemoglobin concentration (MCHC) and neutrophil count.
Coagulation (Screening, Baseline, D7, D14, W4 and 4 weekly thereafter)	Prothrombin time (PT), partial thromboplastin time (PTT), and International Normalized Ratio (INR).
Clinical Chemistry (Screening, then fasting at Baseline, D7, D14, W4 and 4 weekly thereafter)	Sodium, potassium, chloride, bicarbonate, blood urea nitrogen, creatine phosphokinase, creatinine, total protein, albumin, serum amylase (fractionated if > upper limit of normal (ULN)), lipase, phosphate, GGT, AST, ALT, alkaline phosphatase, total bilirubin, calcium, uric acid, glucose and insulin. CRP and C-peptide will be included at Baseline, W4, W12 and W24 only.
Serum lipid panel (Baseline, D7, D14, W4 and 4 weekly thereafter)	Total cholesterol, triglycerides, high and low density lipoproteins
Blood glucose (average) (Screening, W12 and W24)	HBA1c
Urine (Screening only)	Specific gravity, protein, glucose, blood, leukocytes, pH, ketones, bilirubin, urobilinogen, nitrites

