### 12.6.2 Clinical Laboratory Parameters

Routine samples are being collected for assessment of clinical chemistry and hematology. Summary tables at each time point and by toxicity grade will be presented by dose level. All data will be listed.

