### 12.6.3 Vital Signs

Vital signs are being assessed frequently across the duration of the study. Summary tables will be produced for each sign (temperature, heart rate, respiratory rate, systolic and diastolic blood pressure) and by toxicity grade. All data will be listed.

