**APPENDIX A – Laboratory Abnormalities, continued**

Serum	Mild (Grade 1)	Moderate (Grade 2)	Severe (Grade 3)	Potentially Life Threatening (Grade 4)**
Total Protein – Hypoproteinemia g/dL	5.5 – 6.0	5.0 – 5.4	< 5.0	--
Alkaline phosphate – increase by factor	1.1 – 2.0 x ULN	2.1 – 3.0 x ULN	3.1 – 10 x ULN	> 10 x ULN
Liver Function Tests –ALT, AST increase by factor	1.1 – 2.5 x ULN	2.6 – 5.0 x ULN	5.1 – 10 x ULN	> 10 x ULN
Bilirubin – when accompanied by any increase in Liver Function Test increase by factor	1.1 – 1.25 x ULN	1.26 – 1.5 x ULN	1.51 – 1.75 x ULN	> 1.75 x ULN
Bilirubin – when Liver Function Test is normal; increase by factor	1.1 – 1.5 x ULN	1.6 – 2.0 x ULN	2.0 – 3.0 x ULN	> 3.0 x ULN
Cholesterol	201 – 210	211 – 225	> 226	---
Pancreatic enzymes – amylase, lipase	1.1 – 1.5 x ULN	1.6 – 2.0 x ULN	2.1 – 5.0 x ULN	> 5.0 x ULN

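### The SAP omits, undeclared, the protocol's toxicity-grade laboratory and vital-sign tables, so no planned table counts patients by size of ALT/AST worsening; PT, PTT and INR have no safety table

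*SAP*

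**What the plan says.** Protocol 4.2 makes changes in vital signs and laboratory parameters part of the primary safety endpoint. Protocol 12.6.2 opens with "Routine samples are being collected for assessment of clinical chemistry and hematology" and then commits to a format: "Summary tables at each time point and by toxicity grade will be presented by dose level". Protocol 12.6.3 does the same for vital signs: "Summary tables will be produced for each sign (temperature, heart rate, respiratory rate, systolic and diastolic blood pressure) and by toxicity grade". Appendix A supplies the scale. Its row "Liver Function Tests –ALT, AST increase by factor" puts Grade 1 at 1.1–2.5, Grade 2 at 2.6–5.0, Grade 3 at 5.1–10 and Grade 4 above 10 × ULN.

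SAP 8.5 says: "Serum biochemistry parameters will be summarised with change from Baseline and the count of clinically significant values and tabulated by visit". It adds a shift table "showing the number of normal values, abnormal (both above and below normal range) but not clinically significant, clinically significant", the last category also split into above and below range. Haematology is handled the same way. SAP 8.4 gives vital signs as change from Baseline by visit and arm. Toxicity grade appears in neither section and in no laboratory or vital-sign entry of the SAP section 12 table list. SAP section 10 names no departure from the protocol and leaves all of them to the study report.

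Protocol Table 3 lists PT, PTT and INR as a safety panel separate from hematology. SAP 8.5 and the safety part of the table list cover serum biochemistry, haematology and screening urinalysis, with no coagulation entry.

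**The concern.** Raised transaminases at entry are foreseeable here. SAP 7.2 splits patients at 1.5 × ULN for ALT, and the laboratory exclusions in protocol 6.3 set no ALT or AST ceiling. A table whose categories turn on being inside or outside the normal range says little about patients who start outside it. What is left is the clinical-significance flag, presumably the investigator's, since protocol 10.5 has the investigator review every value.

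Transaminases also have a history in this product class. Protocol 3.5.1.2 cites an earlier volunteer study with "transient moderate elevations in serum levels of hepatic transaminases in volunteers who received bovine immunoglobulin concentrates prepared against" *E. coli* (5 of 10) and rotavirus (2 of 10). The protocol calls these transient and attributes them to a high-protein hospital diet. That is weak evidence of harm. It is still a reason to compare graded rises between randomised arms, because a placebo comparison can test that attribution. Without the tables, the primary safety comparison for liver enzymes would rest on averages, extremes and an undefined judgement.

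**Working it through.** The plan gives no figure to reproduce, so the check sets the two documents side by side and counts what each table can distinguish.

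**Step 1. Promised against planned.**

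| Output | Protocol | SAP |
|---|---|---|
| Laboratory tables by grade | 12.6.2: yes | 8.5 and table list: none |
| Vital signs by grade | 12.6.3: yes | 8.4 and table list: none |
| PT, PTT, INR as safety data | Table 3: collected; 12.6.2 does not name them | none; INR only inside MELD |

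**Step 2. Upward moves open to a patient already above range.** This takes the SAP table as a within-patient cross-classification, the favourable reading. Appendix A has four grades above normal, so the upward moves number 4 × 3 / 2 = 6 (1→2, 1→3, 1→4, 2→3, 2→4, 3→4). The SAP table has two above-range states, so there is 2 × 1 / 2 = 1 move (not clinically significant → clinically significant). A patient already flagged at Baseline has none.

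**Step 3. Illustrative patients (assumed values).**

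| ALT, × ULN | Appendix A | SAP shift table | Effect on mean change, arm of 40 |
|---|---|---|---|
| 1.5 → 4 | Grade 1 → 2 | only if the flag changes | (4 − 1.5)/40 = 0.0625 × ULN |
| 2 → 6 | Grade 1 → 3 | only if the flag changes | (6 − 2)/40 = 0.10 × ULN |
| 4 → 11 | Grade 2 → 4 | only if the flag changes | (11 − 4)/40 = 0.175 × ULN |

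The ULN source matters. Appendix A names none, while protocol 4.2 uses ALT limits of 19 IU/L for women and 30 IU/L for men. Take a rise from 60 to 240 U/L:
- Assumed ULN 40: 60/40 = 1.5 and 240/40 = 6.0, Grade 1 → 3.
- ULN 30: 60/30 = 2.0 and 240/30 = 8.0, Grade 1 → 3.
- ULN 19: 60/19 = 3.2 and 240/19 = 12.6, Grade 2 → 4.

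**Step 4. How many patients this touches.** The documents give no proportion with raised ALT or AST at entry. If it were 60–90% (an assumption), then 0.6 × 40 = 24 to 0.9 × 40 = 36 patients per arm would have the flag as their only upward move.

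**Step 5. Whether other outputs supply the count.**
- The summaries (SAP 3.3, 8.5) include quartiles, minimum and maximum by visit. An extreme shows, but not how many patients had one, and transient rises at different visits are spread over several rows.
- Counts of clinically significant values use the same flag.
- Under protocol 10.5, laboratory abnormalities without symptoms are generally not adverse events unless clinically significant, so the severity tables in SAP 8.2 depend on a similar judgement.
- The categorical ALT and AST tables in SAP section 12 count normal ALT or reductions of 5–30%. None counts increases.
- SAP 3.3 uses an unscheduled value only when the preceding scheduled one is missing, so an unscheduled peak may reach only the listings.

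**Step 6. Coagulation.** Protocol Table 1 schedules draws at Screening, Baseline, D7, D14, W4, W8, W12, W16, W20, W24 and W28, which makes 11. MELD is scheduled at Baseline, W12 and W24, which makes 3. INR from the other 11 − 3 = 8 draws enters no planned table, and PT and PTT enter none at all.

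**The case against.** A reader might infer that the SAP tables cannot show ALT or AST worsening at all. The documents do not support that. The shift table has a clinically significant category, so a patient with a raised baseline can move up. Change from Baseline is summarised with minimum and maximum. ALT and AST are also tabulated by visit within baseline-ALT subgroups, clinically significant abnormalities can become adverse events and be tabulated by maximum severity, and all data are listed. This stands: worsening is not invisible. What is missing is its size, counted in patients per arm.

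A reader might also infer that the SAP has withdrawn the protocol's grades. It says it is based on protocol version 1.3 and is silent on grades, so omission is all that can be claimed.

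On coagulation, protocol 12.6.2 names only chemistry and hematology, and Appendix A has no PT, PTT or INR grade. No promised coagulation table has been dropped. The gap is against Table 3 and the primary safety endpoint, and it is the weaker half of the point.

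The volunteer findings do not establish that the product raises transaminases, given how the protocol qualifies them. Nor is raised ALT required for entry: Amendment 3 removed that requirement.

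**Conclusion.** The point holds as a reporting gap. Two grade-based outputs promised in protocol 12.6.2 and 12.6.3 are absent from the SAP and the absence is not declared. For ALT and AST above normal, the SAP shift table offers one upward move where Appendix A offers six, and that move depends on an undefined flag. No planned table gives patients per arm by worst post-baseline grade. Separately, a Table 3 safety panel with 11 scheduled draws has no safety table.

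The move counts and the document comparison need no assumption beyond the favourable reading of the shift table. The ULN of 40 U/L, the 60–90% raised at entry and the example values are illustrations only. It would go too far to say that the trial could never state the number of meaningful rises, because the listings hold the values. But a count first defined after unblinding would be post hoc, on a primary safety endpoint. The efficacy analysis is unaffected.

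**What to change.** Amend the SAP before unblinding:

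- **SAP 8.5, laboratory.** For the Safety population by arm, add the by-visit Appendix A grade summaries that the protocol promises. Add a cross-tabulation of baseline grade against worst post-baseline grade, unscheduled values included, for the graded analytes and at least for ALT, AST and bilirubin. The cross-tabulation goes beyond the protocol's wording, but it is what answers the safety question. State the ULN source, and a rounding rule for values between bands (for example between 2.5 and 2.6 × ULN).
- **SAP 8.5, coagulation.** Add PT, PTT and INR to the by-visit summaries and shift tables.
- **SAP 8.4.** Add the vital-sign tables by grade.
- **Existing shift table.** Keep it as a supplement, and state who assigns clinical significance and on what basis.
- **SAP section 12.** List the new tables. If any promised grade table is deliberately left out, say so in SAP section 10.

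The cost is SAP wording and a few more programmed tables. All the data are already being collected, and no visit, sample or procedure changes.
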